Patients lost to follow-up before experiencing EDA will be considered as not having had the event. A sensitivity analysis with the maximum bias assumption will be conducted by considering missing data (discontinuation of follow-up before the end of the 2-year follow-up with NEDA) in the interventional arm as failures (non-responders = EDA) and those in the control arm as successes (responders = NEDA).

The rate of EDA in both arms will be estimated and then compared between the two treatment arms using mixed-effects logistic regression (random center effect). The treatment arm will be the factor of interest in the model. Adjustment will be made for randomization stratification factors (center, contrast enhancement on diagnostic brain and spinal cord MRI), known prognostic factors listed in section 4.1.4 of the protocol (Age, Gender, Presence of contrast enhancement on the reference MRI, Lesion load in FLAIR in mm³, Number of lesions with contrast enhancement on the reference MRI, EDSS score at baseline), and the time between CIS and the first administration of the treatment, which varies among patients (from a few days to 95 days = maximum of 90 days between CIS and the reference MRI and the first administration of the study treatment, which takes place on the first Saturday post-MRI). Adjustment for the center effect will be performed by considering the center as a random effect in the model (Kahan 2014, Kahan et al. 2015, Edgar et al. 2021).

The number of lesions with contrast enhancement on the reference MRI could not be determined quantitatively. This information is provided by recording the presence of contrast enhancement with a precision level in 3 modalities (similar to the diagnostic MRI): no lesions with contrast enhancement, one lesion with contrast enhancement, and at least two lesions with contrast enhancement. This information will be used as an adjusting variable only if it is not significantly associated with contrast enhancement on the diagnostic MRI (a randomization stratification factor), for which an adjustment is performed. The statistical significance of the association will be assessed using the Chi-square test or Fisher's exact test if the Chi-square test is not applicable, with a significance level set at < 0.05.

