Furthermore, the lesion load in FLAIR in mm³ (reference MRI) is available only for 258 out of 316 patients (those for whom the MRI images could be retrieved). Moreover, obtaining this volume is not reliable because the software does not provide a sufficiently precise estimate. Therefore, no adjustment will be made for the lesion load, and the number of T2/FLAIR lesions on the reference MRI will be used instead as an indicator of lesion load (in 2 modalities: <9 lesions, >= 9 lesions).

In the event of the use of an incorrect stratum during randomization (randomization performed for the stratum with contrast enhancement on the diagnostic MRI while the true value was an absence of contrast enhancement, and vice versa), the analyses will be adjusted for the contrast enhancement value on the diagnostic MRI (Yelland et al., 2022). The stratum error rate will be described by arm.

Primary Analysis (Time to EDA)

Time to EDA is the duration between the date of the first administration of the experimental treatment and the date of EDA.

Date of EDA is:

- The date of the "conversion MRI" for patients with EDA determined by the appearance of NEL on MRI without having a relapse during the follow-up,

- The date of the first symptoms of a relapse for patients with EDA determined by a new relapse without the appearance of NEL on MRI during the follow-up,

- The earlier of the two dates between the date of the first symptoms and the date of the MRI showing NEL for patients who have both a relapse and NEL on MRI during the follow-up.

Patients lost to follow-up or not showing EDA during the follow-up will be right-censored at the date of the last news. The endpoint date will be established for each patient at the date of the end-of-study visit conducted 24 months (2 years) after inclusion.

Time to EDA in both arms will be graphically represented using the Kaplan-Meier method.

The proportional risk of EDA in the experimental arm compared to the placebo arm will be estimated along with its 95% confidence interval using a random-effects Cox model (random center effect) after checking the proportional hazards assumption. Adjustment will be made for the same variables as those used when analyzing the rate of EDA.

Secondary Analyses

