 - Treatment arm (explanatory variable of interest)
 - Center as a random effect (multiple patients per center)
 - Patient as a random effect (multiple measurements per patient)
 - Visit (temporal chronological variable)
 - Interaction between the treatment arm and the presence of a relapse during follow-

up

- A second mixed-effects regression model will be used to compare the M24 scores of the outcome measures while adjusting for baseline scores (M0):
 - M24 score (outcome variables)
 - Treatment arm (explanatory variable of interest)
 - Center as a random effect (multiple patients per center)
 - M0 score (adjustment variable)

- Interaction between the treatment arm and the presence of a relapse during follow-up

Secondary Objective F: Evaluate treatment tolerance on:

a. The occurrence of AEs and SAEs

- b. Pharmacological measurement of serum concentrations of 25(OH)D2 and 25(OH)D3
- c. Measurement of serum calcium, urinary calcium, and renal function

The number of AEs and SAEs per patient will be described by arm.

For points b and c, a mixed-effects regression model will be used to compare the evolution of measurements during follow-up. The model variables will include:

- Measurements at different visits (outcome variable)
- Treatment arm (explanatory variable of interest)
- Center as a random effect (multiple patients per center)
- Patient as a random effect (multiple measurements per patient)
- Visit (temporal chronological variable)

Secondary Objective G: Initial formulation: Correlate the variation in clinical and imaging parameters with the initial level and changes in the levels of 25(OH)D2 and 25(OH)D3 under treatment.

Reformulated Objective G1: Study the link between the severity of impairment (parameters measured by the baseline MRI, such as the number of lesions, EDSS score) and the vitamin D level measured during pre-screening (25(OH)D2 and 25(OH)D3).

A mixed-effects regression model will be estimated. The model variables will include: - Severity of impairment at inclusion (outcome variable). Several variables will be successively modeled: binary variables for MRI parameters (using a logistic regression model) and a quantitative variable for the EDSS score.

- Levels of 25(OH)D2 and 25(OH)D3 at pre-inclusion (explanatory variables of interest)
- Treatment arm (adjustment variable)
- Center as a random effect (multiple patients per center)

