Reformulated Objective G2: Study the link between the occurence of EDA and vitamin D levels (25(OH)D2 and 25(OH)D3) during follow-up.

A mixed-effects regression model will be estimated. The model variables will include:

- Occurrence of EDA (relapse or MRI) (outcome variable)
- Treatment arm (adjustment variable)
- Center as a random effect (multiple patients per center)

- Patient as a random effect (multiple measurements per patient)

- Levels of 25(OH)D2 and 25(OH)D3 measured during follow-up (explanatory variables of interest)

- Visit (temporal chronological variable)

Objectives H, I, and J do not require statistical analyses and involve the establishment of biobanks.

Secondary Objective K: Estimate the discordance rate between the presence of NEL on follow-up MRI scans determined by the neurologist during the study and the result of the centralized MRI analysis performed at the end of the study (EDA not confirmed retrospectively or, conversely, detection of EDA not identified during the study). Additionally, estimate the rate of patients retrospectively identified as erroneously included based on centralized MRI reevaluation (inclusion criterion MRI not verified during centralized reading of the baseline MRI).

Discordance between decisions made during the study by neurologists and the results of centralized reevaluation analyses will be determined for each patient throughout his followup. The discordance rate will be estimated and presented with a 95% confidence interval.

The rate of patients retrospectively identified as erroneously included will also be estimated and presented with a 95% confidence interval.

Anticipated Level of Significance:

A difference will be considered statistically significant when the significance level of the test is less than or equal to 0.05.

Method for Handling Missing, Unused, or Invalid Data:

For the analysis of the primary outcome, if a patient is lost to follow-up without experiencing EDA, they will be considered as NEDA at the end of the 2-year follow-up and censored at the date of the last known status.

Regarding the adjustment variables in the primary analysis:

- If the gadolinium-enhancement status at the diagnostic MRI scan is unknown for a given patient, the missing data will be imputed by the gadolinium-enhancement status at the

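### The models for Objectives C, D, E and F(b, c) leave out the enhancement stratum used in randomisation, which can make their inference slightly conservative

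*SAP*

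**What the plan says.** Under Primary Analysis (Rate of EDA) the SAP states: "Adjustment will be made for randomization stratification factors (center, contrast enhancement on diagnostic brain and spinal cord MRI", followed by the prognostic factors and the time from CIS to first dose. Primary Analysis (Time to EDA) carries the same variables into the Cox model.

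Under Secondary Analyses, Objectives C, D and E share two models. The first, for repeated scores, lists arm, centre and patient as random effects, visit, and an interaction of arm with relapse during follow-up. The second, for the M24 score, lists arm, centre as a random effect, "M0 score (adjustment variable") and the same interaction.

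For Objective F the plan says: "For points b and c, a mixed-effects regression model will be used to compare the evolution of measurements during follow-up". That list has arm, centre and patient as random effects, and visit. Point (a) has no model: "The number of AEs and SAEs per patient will be described by arm".

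Each of the three secondary lists contains "Center as a random effect (multiple patients per center"). None contains enhancement.

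**The concern.** When allocation is balanced within strata, the variation between strata does not contribute to the error of the arm comparison. A model that leaves the stratum out still counts that variation as residual noise, so its standard errors overstate the true uncertainty. The SAP respects this for the primary endpoint but, for EDSS, PASAT, the questionnaires, vitamin D levels, calcium and renal function, keeps only one of the two stratification factors. At stake is a small amount of precision on secondary outcomes, and agreement between how patients were randomised and how they are analysed.

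**Working it through.** **No figure to reproduce.** The SAP states no power, standard deviation, effect size or interval width for Objectives C to F. The check is therefore a comparison of the variable lists, then a sensitivity calculation.

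**Step 1: the lists side by side.**

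| Analysis | Centre | Enhancement | Other terms besides arm |
|---|---|---|---|
| EDA rate, time to EDA | random | adjusted | prognostic factors, time from CIS |
| C, D, E: repeated scores | random | not listed | patient (random), visit, arm × relapse |
| C, D, E: M24 score | random | not listed | M0 score, arm × relapse |
| F(b, c) | random | not listed | patient (random), visit |
| F(a) | no model | no model | descriptive |

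**Step 2: does another sentence repair the gap?** Where the wrong stratum was used at randomisation, "the analyses will be adjusted for the contrast enhancement value on the diagnostic MRI". That rule is conditional on a stratum error and sits under the primary analysis. The rule for unknown enhancement status, under Method for Handling Missing, Unused, or Invalid Data, is introduced as one for the primary analysis. Neither adds enhancement to the secondary models.

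**Step 3: size for a simple arm effect.** Let R² be the share of outcome variance that enhancement explains after the other terms. With arms balanced within strata:

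- standard-error ratio, omitted to included = 1/√(1 − R²)
- type I error with the stratum omitted = 2 × [1 − Φ(1.96/√(1 − R²))]
- patient equivalent = 316 × R²

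The level is from the SAP: "A difference will be considered statistically significant when the significance level of the test is less than or equal to 0.05". Two-sided testing is assumed. The 316 is the patient count given under Primary Analysis (Rate of EDA) and is used only for scale. With 1:1 allocation (assumed), the 95% half-width with the stratum omitted is 1.96 × √(4/316) = 0.2205 SD.

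| R² (assumed) | SE ratio | Type I error, omitted | Half-width if included (SD) | Patient equivalent |
|---|---|---|---|---|
| 0 | 1.000 | 0.050 | 0.2205 | 0 |
| 1% | 1.005 | 0.049 | 0.2194 | 3 |
| 2% | 1.010 | 0.048 | 0.2183 | 6 |
| 5% | 1.026 | 0.044 | 0.2149 | 16 |
| 10% | 1.054 | 0.039 | 0.2092 | 32 |

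**Step 4: what such R² values mean.** With a share p of patients enhancing and a mean difference of d residual SDs between strata, R² = p(1 − p)d²/[1 + p(1 − p)d²]. At p = 0.4 (assumed), d = 0.2 gives a ratio of 1.005, d = 0.3 gives 1.011, d = 0.5 gives 1.030 and d = 0.7 gives 1.057.

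**Step 5: repeated-measures models.** With four visits and intraclass correlation ρ (assumed), the variance of a patient's mean is ρ + (1 − ρ)/4, and the stratum adds p(1 − p)d², with d now in total SDs. At p = 0.4, d = 0.5 and ρ = 0.5 the ratio is √[(0.625 + 0.06)/0.625] = 1.047; at ρ = 0.8 it is √[(0.85 + 0.06)/0.85] = 1.035. At d = 0.2 the ratio lies between 1.006 and 1.008.

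**Step 6: simulation.** The M24 model without the relapse interaction was simulated with N = 316, 33 centres fitted as fixed effects, blocks of 4 within centre and stratum, p = 0.4 and 2,500 runs. All of these except N are assumptions.

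| d | SE ratio | Type I, omitted | Type I, included |
|---|---|---|---|
| 0 | 0.9995 | 0.048 | 0.047 |
| 0.2 | 1.004 | 0.041 | 0.041 |
| 0.5 | 1.029 | 0.042 | 0.047 |
| 1.0 | 1.114 | 0.034 | 0.054 |

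The Monte Carlo error at a rate of 0.05 is √(0.05 × 0.95/2,500) = 0.004, so only the largest d shows a clear drop below 0.05 that is specific to omitting the stratum. The standard-error ratios agree with the formula.

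**The case against.** The strongest reply is that no loss is shown. Widening needs an association between enhancement and the outcome, and the SAP gives none for any of these outcomes. It treats enhancement as prognostic in the EDA analysis only; nothing in it suggests that enhancement predicts 25(OH)D, calcium or renal function. In the M24 model the M0 score already absorbs part of any stratum effect. This stands: the size is conditional.

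The formula is also only approximate for C, D and E. With an arm × relapse term, the arm coefficient refers to one relapse group, and randomisation does not guarantee stratum balance within that group. The 316 may overstate the patients in the M24 models, since no imputation is planned for secondary outcomes. Both points stand. They limit the precision of the figures but do not explain the omission.

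The secondary models also leave out most of the primary model's prognostic factors, so a deliberately lean set is possible. That explains leaving out age or lesion count better than it explains leaving out a factor that the allocation itself used, when the other such factor is kept.

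Finally, the same lists raise larger questions: the relapse interaction conditions on an event after randomisation, and models meant to compare evolution list no arm × visit term. These are separate points and do not answer this one.

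**Conclusion.** The inconsistency is real: three secondary models drop one of the two stratification factors that the primary models keep, and nothing in the SAP restores it. The consequence is minor. If enhancement is prognostic after the other terms, standard errors and p-values for the arm effect are slightly conservative, by about 0.5% at R² = 1%, 2.6% at 5% and 5.4% at 10%, and by nothing at zero. As a matter of judgement, an association is most plausible for EDSS and least for 25(OH)D, calcium and renal function. The figures rest on assumed R², balanced allocation within strata and a simple arm effect.

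A reader might infer three stronger things that the document does not support:

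- That the intervals are in fact wider. This needs an association the SAP never quantifies, and the SAP specifies no intervals for these models.
- That all of Objective F is affected. F(a) has no model.
- That the tests are invalid or too liberal. Under the stated assumptions the error runs the other way.

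**What to change.** Add contrast enhancement on the diagnostic MRI as a fixed effect to both models for Objectives C, D and E and to the model for F(b, c), with the definition used in the primary analysis, including the use of the true value where the wrong stratum was applied.

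State that the fallback for unknown enhancement status under Method for Handling Missing, Unused, or Invalid Data also applies to these models. It ends with the stratum recorded at randomisation, so no patient need be dropped. Without this extension, missing covariate values could cost more patients than the adjustment gains.

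The cost is a sentence or two of SAP text and one degree of freedom per model. The variable is already needed for the primary analysis. F(a) stays as it is.

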Statistical Analysis Plan

December 21st, 2023

NCT01817166

PHRC-N/2012/ET-01

Efficacy of Cholecalciferol (Vitamin D3) for Delaying the Diagnosis of MS After a Clinically Isolated Syndrome

Final detailed statistical analysis plan drafted before data lock and before the commencement of statistical analyses.

An initial data analysis will provide a description of each arm. Statistical results will be presented using mean and standard deviation for quantitative variables with a Gaussian distribution, and median and interquartile range for other quantitative variables. For qualitative variables, frequencies and associated percentages will be presented.

Demographic, clinical (initial relapse), radiological (diagnostic MRI), and biological (lumbar puncture, vitamin D) data will be described. In particular, it will be determined for each patient whether the diagnostic criteria of McDonald 2017 are met at inclusion (Thompson et al., 2018).

The statistical analysis will be conducted by the BESPIM of the CHU de Nîmes using R 4.1.1 or a later version (R Core Team (2021). R Foundation for Statistical Computing, Vienna, Austria).

Primary Analysis (Rate of EDA)

The primary objective is to assess the efficacy and tolerance over 2 years of treatment with Cholecalciferol (Vitamin D3) in patients who have experienced a clinically isolated syndrome at high risk of multiple sclerosis (CIS, according to the McDonald criteria of 2005). This efficacy will be measured by comparing the risk of conversion to relapsing-remitting multiple sclerosis (RRMS) within 2 years after CIS, according to 2005 McDonald criteria (new lesions on follow-up brain and spinal cord MRIs or new relapses) (McDonald et al., 2001; Polman et al., 2005), between the arm receiving Cholecalciferol and the arm receiving the placebo.

Following the actual diagnostic criteria for MS (McDonald 2017), most patients present with a diagnosis of active MS and conversion corresponds to the current concept of EDA (evidence of disease activity defined by clinical relapses or imaging (gadolinium-enhancing lesions or new or unequivocally enlarging T2/FLAIR lesions) (Lublin et al., 2013) an "no conversion" corresponds to NEDA (no evidence of disease activity). Hence, the event will be the occurrence of EDA within the two years of follow-up (relapse and/or appearance of new or enlarging lesions (NEL) on follow-up MRIs at 3, 12, and 24 months).

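### Secondary Objective F models average calcium and renal levels but commits to no count of patients with abnormal values, so an affected minority could go unreported

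*SAP*

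**What the plan says.** Secondary Objective F covers tolerance in three items: the occurrence of AEs and SAEs (a), serum 25(OH)D2 and 25(OH)D3 (b), and "Measurement of serum calcium, urinary calcium, and renal function" (c).

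- **Item a:** "The number of AEs and SAEs per patient will be described by arm". No between-arm comparison is planned and the form of the description is not fixed. The SAP's opening section sets the general rule for quantitative variables: mean and SD if Gaussian, and "median and interquartile range for other quantitative variables".
- **Items b and c:** "For points b and c, a mixed-effects regression model will be used to compare the evolution of measurements during follow-up". The outcome is the measured value at each visit. The explanatory terms are arm, visit, and random effects for centre and patient. No arm-by-visit interaction is listed.

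No section of the SAP plans a count or proportion of patients with an abnormal calcium or renal value, a worst-value or shift summary, a proportion of patients with at least one AE or SAE, or a breakdown of AEs by type.

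**The concern.** Laboratory safety is mainly a question of how many patients leave the acceptable range, which concerns the tail of the distribution. The planned model estimates a difference in average level. If most treated patients are unchanged and a few rise markedly, the average hardly moves. If the rise appears at only one visit, averaging over visits dilutes it further.

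The AE description does not reliably fill the gap. Counts per patient are usually skewed, so the SAP's general rule points to median and IQR. When fewer than a quarter of patients have any event, that summary reads 0 (0-0). An abnormal value recorded as an AE would be one unlabelled event within a patient's total.

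At stake is the tolerance statement. The report could follow the SAP exactly, show no difference in mean calcium, and never state how many patients in each arm had raised values. A count added after unblinding would be post hoc. The efficacy results are not affected.

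**Working it through.** The SAP gives no sample size, event rate or power for tolerance, so there is no figure to reproduce. What follows is an illustration for serum calcium.

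**Inputs**
- 316 patients: the denominator given for the lesion-load data in the SAP's section on the rate of EDA. Arm sizes are not stated; n = 158 per arm (316 / 2) is assumed.
- Significance level 0.05: the SAP's section on the level of significance; two-sided is assumed.
- Assumed, not in the SAP: between-patient SD 0.08-0.12 mmol/L; a fraction f = 5% of treated patients raised by r = 0.3-0.4 mmol/L at every visit; all others unchanged.

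**1. Shift in the mean.** f × r = 0.05 × 0.3 = 0.015 and 0.05 × 0.4 = 0.020 mmol/L.

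**2. Power on the mean, equal SD in both arms.** SE = SD × √(2/158); z = shift / SE; power = Φ(z − 1.96).

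**3. The same with the variance that the affected minority adds.** Treated-arm variance = SD² + f(1 − f)r²; SE = √[(SD² + treated-arm variance)/158]. At SD 0.10 and r = 0.3, the treated-arm variance is 0.0100 + 0.0475 × 0.09 = 0.0143, so SE = 0.0124 and z = 1.21.

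| SD | Rise | Shift | Power, step 2 | Power, step 3 |
|---|---|---|---|---|
| 0.08 | 0.3 | 0.015 | 38% | 30% |
| 0.08 | 0.4 | 0.020 | 60% | 42% |
| 0.10 | 0.3 | 0.015 | 27% | 23% |
| 0.10 | 0.4 | 0.020 | 43% | 33% |
| 0.12 | 0.3 | 0.015 | 20% | 18% |
| 0.12 | 0.4 | 0.020 | 32% | 26% |

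The range is 20-60% without the added variance, 18-42% with it, and 18-60% overall.

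**4. A transient rise.** Assume four visits with within-patient correlation 0.5, and a rise of 3 SD in 5% of treated patients at one visit only. The shift in the visit average is 0.05 × 3 / 4 = 0.0375 SD, and power is about 6%.

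**5. Counting patients instead.** The placebo abnormal rate is p0, and an extra 5% of otherwise normal treated patients become abnormal, so p1 = p0 + 0.05(1 − p0). Fisher's exact test, with power by summing the two binomials at 158 per arm:

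| Placebo rate | Treated rate | Fisher power |
|---|---|---|
| 0% | 5.0% | 81% |
| 1% | 5.95% | 59% |
| 2.5% | 7.4% | 42% |
| 5% | 9.75% | 29% |
| 10% | 14.5% | 18% |

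For single outcomes, 8/158 against 0/158 gives p = 0.007, and 8/158 against 2/158 gives p = 0.10.

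**6. What a count shows whatever the test says.** 8/158 is 5.1% (exact 95% CI 2.2% to 9.7%); 0/158 has an upper limit of 2.3%. A mean difference of 0.015-0.020 mmol/L reveals neither figure.

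**7. AEs as median and IQR.** If 37 of 158 patients (23%) have one event and the rest none, the quartiles are 0, 0 and 0.

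**The case against.** The strongest reply is that a count is not a better test in general. The p = 0.007 for 8 against 0 needs a placebo arm with no abnormal value at all, which is unlikely for a measure such as at least one value out of range across repeated visits. At placebo rates of a few percent, Fisher power falls into the range found for the mean. This stands: a reader might infer from the best case that counting gains power, and step 5 does not support that.

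Second, a reader might infer that the AE plan cannot show the proportion of patients affected. That goes too far. A frequency table of events per patient, including zero, would show it, and the SAP does not exclude one. It simply does not commit to one.

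Third, the protocol is not shown. It may hold laboratory safety limits, and may require abnormal values to be recorded as AEs. That bears on which limit to use and on how AEs are collected. It does not change the summary that this SAP fixes, and the SAP plans no AE breakdown by type in which such events would be visible.

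Fourth, the primary objective is worded to "assess the efficacy and tolerance over 2 years of treatment", and a reader might infer a flaw in the primary analysis. But the next sentence defines a measure for efficacy only ("This efficacy will be measured by comparing the risk of conversion to relapsing-remitting multiple sclerosis (RRMS) within 2 years after CIS"), and tolerance is analysed under a secondary objective. That is a separate labelling inconsistency and does not show the mixed model to be wrong.

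Finally, the SAP nowhere says that a non-significant mean difference will be read as evidence of safety.

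**Conclusion.** The point holds as a gap in what Objective F commits to report. For serum calcium, urinary calcium and renal function, the only planned analysis is a model of measured values whose arm term is an average over visits, and no count of affected patients is promised. For AEs and SAEs, the format is left open and could hide how many patients had an event.

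Under the assumptions above, a 5% minority with a sustained rise would be detected through the mean with about 18-60% power, and a rise at one visit of four with about 6%. The SD, rise, affected fraction, arm size and visit structure are all assumed, so these figures show the direction of the problem and do not predict this trial. The case rests on making affected patients visible. The planned models are not invalid, and no efficacy result depends on this. It should be changed, but it is a matter of safety reporting.

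**What to change.** Add to Secondary Objective F, by arm:

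- for each of serum calcium, urinary calcium and renal function, the number and proportion of treated patients with at least one post-baseline value beyond the protocol's own safety limit (or the laboratory reference limit where the protocol has none), in the direction of concern, with the risk difference and 95% CI;
- the number and proportion of patients with at least one AE, and with at least one SAE.

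Keep the mixed models as supportive. Name the source of each limit in the SAP before data lock, so that it is not chosen after the results are seen.

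The cost is a few lines of SAP wording and one table from data already collected. The downside is that intervals will be wide when events are rare. They should be shown as they are, and a wide interval or a non-significant difference should not be read as absence of harm.

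### The Objective F laboratory model omits a pre-treatment covariate and an arm-by-visit term, and leaves open whether the pre-treatment visit is an outcome row

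*SAP*

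**What the plan says.** Under Secondary Objective F, adverse events are only described by arm. The laboratory outcomes, that is 25(OH)D2 and 25(OH)D3 (point b) and "Measurement of serum calcium, urinary calcium, and renal function" (point c), get a single model: "For points b and c, a mixed-effects regression model will be used to compare the evolution of measurements during follow-up".

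The listed terms are:
- outcome: "Measurements at different visits (outcome variable")
- treatment arm
- centre as a random effect
- "Patient as a random effect (multiple measurements per patient")
- "Visit (temporal chronological variable")

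Nothing else is listed.

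Two other parts of the Secondary Analyses bear on this:
- The second model for Objectives C, D and E compares M24 scores and includes "M0 score (adjustment variable").
- Objective G1 uses "the vitamin D level measured during pre-screening (25(OH)D2 and 25(OH)D3"), so a pre-treatment 25(OH)D value exists.

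The SAP nowhere says that calcium or renal function was measured before the first dose. Its opening section names only lumbar puncture and vitamin D as the biological data to be described.

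**The concern.** The stated aim is to compare evolution, but three things that this needs are left out or left open.

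1. **Divergence over time.** With arm and visit as main effects only, the fitted arm profiles are parallel. The model estimates one constant arm difference and cannot show the arms moving apart.
2. **Role of the pre-treatment visit.** The SAP does not say whether it is among the visits modelled. If it is, the arm effect is averaged over a visit at which nobody had been treated.
3. **Pre-treatment value as covariate.** If only follow-up visits are modelled, stable differences between patients stay in the standard error of the arm contrast, and part of any chance baseline difference passes into the estimate.

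Tolerance is named in the SAP's primary objective, and this model is the only planned between-arm comparison of calcium and renal function. Lost precision in a tolerance comparison is not conservative, because a small adverse shift becomes easier to miss.

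**Working it through.** The SAP gives no power, standard deviation or correlation for Objective F, so there is no planned figure to reproduce.

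**Inputs**
- Patients: 316 (SAP, paragraph on FLAIR lesion load). I take n = 158 per arm, assuming 1:1 allocation.
- Follow-up visits with laboratory values: not stated. I take r = 3 from the MRI schedule (3, 12 and 24 months), with 2 and 4 as a check.
- Correlation rho between any two measurements of one patient: not stated. I assume compound symmetry, as the random patient intercept implies, and vary rho.
- Outcome SD set to 1; centre effect left out.

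**Reading A: follow-up rows only**

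Variance of a patient's mean over r visits: v0 = (1 + (r − 1)·rho)/r. After adjustment for one baseline value: v1 = v0 − rho². The SE of the arm contrast is √(2/n)·√v0 or √(2/n)·√v1.

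| rho | v0 | v1 | adjusted/unadjusted SE, √(v1/v0) | equivalent sample size, v0/v1 |
|---|---|---|---|---|
| 0.1 | 0.400 | 0.390 | 0.99 | 1.03 |
| 0.3 | 0.533 | 0.443 | 0.91 | 1.20 |
| 0.5 | 0.667 | 0.417 | 0.79 | 1.60 |
| 0.7 | 0.800 | 0.310 | 0.62 | 2.58 |

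In absolute terms at rho = 0.5, √(2/158) = 0.1125, so the SE falls from 0.1125 × 0.816 = 0.092 SD to 0.1125 × 0.645 = 0.073 SD. The 95% half-width falls from about 0.18 to 0.14 SD. With 2 or 4 visits, the SE ratio at rho = 0.5 is 0.82 or 0.77.

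A chance baseline imbalance passes into the unadjusted contrast with slope rho. At rho = 0.5, an imbalance of 0.2 SD shifts the estimate by 0.5 × 0.2 = 0.10 SD.

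**Reading B: the pre-treatment visit is also an outcome row**

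With no arm-by-visit term, the arm effect is the mean difference over r + 1 rows, one of them untreated. A constant true effect shrinks to r/(r + 1): 75% for r = 3, 67% for r = 2, 80% for r = 4. The variance is (2/n)·(1 + r·rho)/(r + 1).

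For r = 3 and rho = 0.5, the SE is 0.1125 × √0.625 = 0.089 SD. Rescaled for the dilution it is 0.089/0.75 = 0.119 SD, which is 1.63 times the baseline-adjusted 0.073. An imbalance of 0.2 SD shifts the estimate by 0.625 × 0.2 = 0.125 SD.

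**Simulation check** (200 trials, true effect 0.30 SD, rho = 0.5, r = 3)

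| Model | Mean estimate | SD of estimates | Slope on baseline imbalance |
|---|---|---|---|
| A, as listed | 0.302 | 0.092 | 0.47 |
| A, with baseline covariate | 0.302 | 0.073 | −0.03 |
| B, as listed | 0.227 | 0.090 | 0.60 |

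The random patient intercept is in all three models. It does not remove the imbalance in the two models as listed.

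**The case against.** The strongest defence is that an unadjusted repeated-measures comparison in a randomized trial is valid, so a baseline covariate improves efficiency and corrects no error. That stands for reading A. The contrast is unbiased on average, the type I error is 5%, and the standard error already allows for chance imbalance.

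A reader might infer that the plan produces false safety signals. Given a 2-SE baseline imbalance, the unadjusted test would reject in 11% (rho = 0.3) to 32% (rho = 0.8) of cases. Those rates hold only given that imbalance, and one at least that large arises in about 4.6% of randomizations. Nor is a whole imbalance taken for a treatment effect, since only the fraction rho passes through.

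A reader might also infer that the trial is discarding baseline calcium and renal values that it holds. The SAP does not support this, because it documents a pre-treatment value for 25(OH)D only. The precision gain for the other three outcomes depends on whether a pre-dose value was collected.

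The sizes are also modest. The half-width at rho = 0.5 is already about 0.18 SD, and at rho = 0.1 the gain is about 1%. The SAP gives no interval between pre-screening and first dose, so the pre-screening 25(OH)D value may correlate less with later values than compound symmetry assumes.

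Which reading applies cannot be settled from the text. Objective F speaks only of follow-up, whereas Objectives C to E name baseline as well, which favours A. But the first C to E model words its outcome in a parallel way for scores that include baseline, which favours B. That model also has no separate baseline covariate, so Objective F contradicts nothing. What remains is the open specification and the missing arm-by-visit term, which neither reading cures.

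**Conclusion.** The point holds as a low-severity improvement to a secondary tolerance analysis. The listed model does not match its stated aim, because it has no arm-by-visit term, and the role of the pre-treatment visit is undefined.

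If only follow-up rows enter, the cost is precision. The avoidable excess in the SE runs from about 1% (rho = 0.1) through 10% (0.3) and 27% (0.5) to 61% (0.7). If the pre-treatment visit is a row, the arm effect is diluted to about 75%.

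These sizes rest on 3 follow-up visits, compound symmetry and an assumed rho, none of which is in the SAP. The dilution figure also assumes a constant effect from the first follow-up visit.

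**What to change.** In the Objective F model for points b and c:

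- State that the outcome rows are post-treatment visits only.
- Add the pre-treatment value of the same measurement as a covariate. For 25(OH)D2 and 25(OH)D3 this is the pre-screening value already used in Objective G1. For serum calcium, urinary calcium and renal function it is the last pre-dose value, where one was collected. The SAP should say whether one was.
- Add an arm-by-visit term, and say which contrast is reported (for example, the visit-averaged arm difference together with the arm-by-visit test).
- Where the baseline covariate is missing, use the pooled mean with a missing indicator, so that no treated patient is dropped. State that this concerns the covariate only, so it does not conflict with the rule under Method for Handling Missing, Unused, or Invalid Data that other secondary outcomes are not imputed.

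The cost is a short SAP edit and no new data collection. Each outcome model gains a few parameters: with 3 visits, one covariate, one missing indicator and two interaction terms. The SAP describes itself as drafted before data lock. A change made before the lock counts as prespecified; a later one should be labelled as such.
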